9.3.6. Ulcerative Colitis History/Medical History

In order to determine the participant's eligibility to the study, a complete medical history of each participant will be collected and documented during screening. The history should include, recent blood donations (\leq 30 days prior to the screening period), illnesses, and participation in other investigational drug studies.

In addition, a detailed history of the participant's UC, including date of diagnosis, disease severity, hospitalizations, and extraintestinal manifestations (EIMs), will be collected.

9.3.7. Vital Signs

At screening, vital signs (resting HR, systolic and diastolic BP, body temperature, and respiratory rate) will be measured while sitting.

9.3.8. Pulmonary Function Test

Pulmonary function tests including FEV₁ and FVC measurements will be performed. In addition, diffusing capacity of the lungs for carbon monoxide (DLCO) measurements will be performed where locally available (sites where DLCO is not available should consult the Sponsor or Sponsor's delegate).

9.3.9. Ophthalmoscopy and Optical Coherence Tomography

Ophthalmoscopy and OCT will be performed. A general ophthalmologist can do the examination; although, a retinal specialist would be preferred wherever possible. Participants with a history of macular edema or retinopathy are not eligible for the study (Section 4.2).

9.3.10. Clinical Laboratory Assessments

Screening samples for complete blood count (CBC) with differential, platelet count, lymphocyte counts, T lymphocytes, B lymphocytes, natural killer lymphocytes (TBNK) cell counts, serum chemistry, virology, thyroid panel, coagulation, urinalysis, high-sensitivity C-reactive protein (hs-CRP), TB screen, and stool sample should be obtained and results must be available and reviewed prior to randomization. In the case of new clinical laboratory abnormalities detected prior to randomization, the eligibility of the participant should be reconsidered with the guidance of the Medical Monitor.

9.3.11. Proctosigmoidoscopy/Colonoscopy and Modified Mayo Score Derivation

- Proctosigmoidoscopy/colonoscopy must be performed prior to randomization of treatment to allow central reader review (may take approximately 512 days) and confirmation of eligibility. Preferably, proctosigmoidoscopy/colonoscopy should be performed after other criteria for inclusion (eg, laboratory criteria) have been met.
- **Determination of MMS score to qualify for randomization:**
 - The MMS will be evaluated at Day 1. The subscores for stool frequency (SF) and RB are derived from the participant eDiary entries using the scores from the 3 most recent consecutive days within the 7 days prior to the day of bowel preparation (excluding the day of bowel preparation), averaged and rounded to the nearest integer. The scoring will be calculated electronically. Participants who do not have 3 consecutive days of eDiary data within that 7-day period and who do not have a minimum of 7 days of eDiary data prior to bowel preparation are not eligible for randomization. The MMS must be 4 to 9, including an ES ≥ 2 and RB subscore ≥ 1 , for the participant to be eligible for randomization.
 - For the normal SF, it is essential for the participant to be asked to identify how many stools he or she has in a 24-hour period when in remission from UC. Participants should be instructed that a stool is defined as a trip to the toilet when the participant has either a bowel movement, or passes blood alone, blood and mucus, or mucus only. If the participant does not report that he or she has achieved remission, then the participant should be asked to identify the number of stools he or she had before initial onset of signs and symptoms of UC.

9.4. Randomization/Treatment Period

9.4.1. Week 0/Day 1: Pre-randomization

At the Week 0/Day 1 visit (Table 6), prior to randomization, a 12-lead ECG in the supine position and resting vital signs in the sitting position (HR, systolic and diastolic BP, body temperature, and respiratory rate) will be collected. Caffeine and/or nicotine are not permitted within 30 minutes prior to BP measurements.

Participants with the following must not be randomized and should be considered screen failures:

- Sitting vital sign assessment: HR < 50 bpm OR systolic BP < 90 mm Hg OR diastolic BP < 55 mm Hg
- 12-lead ECG showing a second-degree or third-degree AV block, periods of asystole > 3 seconds, PR interval > 200 ms, or QTcF \geq 450 ms (men) or QTcF \geq 470 ms (women).

All predose 12-lead ECGs should be obtained prior to blood sample collection.

Participants who continue to meet all eligibility criteria will be randomized as outlined in Section [6.4](#).

9.4.2. Treatment Period

After randomization, the 12-Week Treatment Period of the study will begin ([Table 6](#)). A study visit window of \pm 3 days is permitted at each visit beginning with Week 2/Day 15 (PFT and OCT assessments have a window of \pm 7 days). Study visits should be scheduled for the morning.

The subscores for SF and RB are derived from the participant eDiary entries. On visits when MMS is calculated, these subscores are derived using the scores from the 3 most recent consecutive days within the 7 days prior to the day of bowel preparation (excluding the day of bowel preparation), averaged and rounded to the nearest integer. If 3 consecutive days are not available, then the average of the 2 most recent consecutive days within the 7 days will be used.

On visits without endoscopy, the SF and RB subscores are derived using the scores from the 3 most recent consecutive days within the 7 days prior to the date of visit, averaged and rounded to the nearest integer. If 3 consecutive days are not available, then the average of the 2 most recent consecutive days within the 7 days will be used.

It is recommended that procedures are performed in a consistent order and at approximately the same time of day for each visit. Below is the recommended sequence of events (refer to Schedule of Assessments, [Table 6](#)):

- Questionnaire administration
- Adverse event review
- Vital signs
- 12lead ECG
- Physical examination
- EIMs
- PFT
- OCT
- Blood sample collection for laboratory tests and predose PK sampling

9.4.2.1. Guidance for Cardiac Monitoring Following Treatment Initiation or Re-Initiation

Pre-randomization (ie, pre-dose/baseline) vital signs (resting HR, systolic and diastolic BP, body temperature, and respiratory rate) will be used as the baseline measurement. The pre-dose HR measurement will be used for comparison to the postdose measurement. It is recommended that participants receive the first dose of study treatment before 12:00 PM (noon).

9.4.2.1.1. First Dose Cardiac Monitoring

In-clinic cardiac monitoring, of at least 4 hours, will occur on Day 1 and will include the following (Table 2):

- Full baseline vital signs (HR, systolic and diastolic BP, body temperature, and respiratory rate) and a 12-lead ECG (taken with the participant in the supine position) will be assessed pre-randomization.
- After the first dose of study treatment on Day 1, participants must remain under observation in the clinic for at least 4 hours.
- At Hours 1, 2, and 3 (\pm 15 minutes) postdose, the HR and systolic and diastolic BP will be assessed with the participant in the sitting position, with the time recorded. If the participant has an HR $<$ 50 bpm or if cardiovascular symptoms develop, then the participant should remain closely monitored, including 12-lead ECGs as clinically indicated, until the Hour 4 discharge assessment.
- At the Hour 4 (\pm 15 minutes) discharge assessment, HR and systolic and diastolic BP will be assessed with the participant in the sitting position and a 12-lead ECG (with the participant in the supine position) will be performed. Participants may be discharged from the clinic after the 4-hour assessment if they meet the criteria described in [Table 3](#). Participants not meeting the discharge criteria will require extended monitoring as described below.
- Participants experiencing a clinically relevant treatment-related symptomatic event (eg, chest pain, dizziness, palpitations, or syncope) associated with reduction of the HR or clinically relevant 12-lead ECG changes at any time during the 4-hour monitoring period must be discontinued from treatment ([Table 4](#)).

Table 2: Procedures to be Performed During the Monitoring Period

Procedure	Predose	Hours 1, 2, 3 Postdose ^a	Hour 4 Postdose ^a
Blood pressure and heart rate ^b	X	X	X
12-lead ECG	X		X
Assess discharge criteria			X

^a Measurements may be taken \pm 15 minutes of the scheduled time.

^b Heart rate is based on vital signs.

ECG, electrocardiogram

Table 3: Discharge Criteria After Cardiac Monitoring

Participants will be released from the clinical site after dosing on Day 1 (but no sooner than 4 hours postdose) when they fulfill the following discharge criteria:
• Heart rate \geq 50 bpm or no more than 10 bpm lower than the predose (baseline) value
• No evidence of second-degree AV block or higher
• No cardiac symptoms (eg, chest pain, dizziness, palpitations, lightheadedness, shortness of breath, or syncope)

Note: Participants should have written instructions on when to return to the clinic and a 24-hour contact phone number to call in the event of any new or worsened cardiovascular symptoms.

AV, atrioventricular; bpm, beats per minute

9.4.2.1.2. Extended Cardiac Monitoring

Participants who do not meet discharge criteria at 4-hours postdose will require extended cardiac monitoring:

- Vital signs will be assessed hourly and 12-lead ECG may be performed, as clinically indicated, until the participant meets the discharge criteria (Table 3).
- The Medical Monitor should be contacted if the participant does not meet the discharge criteria after \geq 4 hours of extended cardiac monitoring.
- Any participant who requires extended monitoring on Day 1 must return on Day 2 for the second dose and will be re-monitored as on Day 1. These participants will be discontinued from study treatment if they do not meet the discharge criteria at 4 hours after the second dose. Extended cardiac monitoring should be continued until the participant meets the discharge criteria (Table 3).
- Participants experiencing a symptomatic event (eg, chest pain, dizziness, palpitations, lightheadedness, shortness of breath, or syncope) at any time during the 4-hour monitoring period that is not associated with either a reduction in HR or clinically relevant change in 12-lead ECG, may be discharged provided they meet the discharge criteria (Table 3), and as deemed appropriate by the Investigator; however, these participants must return on Day 2 for the second dose and will be re-monitored as on Day 1. These participants must be discontinued from treatment if they do not meet the discharge criteria at 4 hours after the second dose on Day 2 and extended cardiac monitoring should be continued until the participant meets the discharge criteria (Table 3).

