5. REMOVAL OF PARTICIPANTS FROM STUDY TREATMENT OR ASSESSMENT

5.1. Discontinuation from Study Treatment

A participant's double-blind treatment may be discontinued for any of the following reasons:

- Adverse event that in the judgement of the Investigator and/or Medical Monitor indicate the participant should not continue study treatment
- Participant noncompliance with the protocol or study treatment that is considered significant by the Medical Monitor
- Investigator decision
- Withdrawal by participant
- Lack of efficacy
- Lost to follow-up
- Study termination by Sponsor
- Other, non-adverse event

A participant's double-blind treatment must be discontinued for any of the following reasons:

- Decline in PFT values (FEV₁ and/or FVC) below 50% of the predicted values
- Confirmed diagnosis of clinically significant macular edema
- Confirmed diagnosis of active TB
- Participants who have a cardiovascular treatment-related symptomatic event (eg, chest pain, dizziness, palpitations, lightheadedness, shortness of breath, or syncope) associated with reduction of the HR or associated with clinically relevant ECG changes at any time during the 4-hour monitoring period on Day 1 or Day 2 (as applicable) (Section 9.4.2.1)
- Participants who have not met the discharge criteria ([Table 3](#)) on Day 1 after \geq 4 hours of extended monitoring, or Day 2 by 4 hours postdose
- Pregnancy (Section 9.9.9)

- Suspected drug induced liver injury as defined by the 2009 FDA Guidance for Industry ([FDA 2009](#))
 - ALT or AST $> 8 \times$ ULN
 - ALT or AST $> 5 \times$ ULN for > 2 weeks
 - ALT or AST $> 3 \times$ ULN and (total bilirubin $> 2 \times$ ULN or international normalized ratio > 1.5)
 - ALT or AST $> 3 \times$ ULN with the appearance of fatigue, nausea, vomiting, right upper quadrant pain or tenderness, fever, rash, and/or eosinophilia ($> 5\%$)

Because transient fluctuations of ALT or AST are common, and progression to severe drug induced- liver injury or acute liver failure is uncommon, automatic discontinuation of study treatment upon finding a greater than $3 \times$ ULN elevation of ALT or AST may be unnecessary. If a drug induced-liver injury is identified, refer to Section [16.6](#) for guidance.

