9.4.2.1.3. Study Treatment Discontinuation Related to Postdose Cardiac Monitoring

A complete list of reasons for study treatment discontinuation is provided in Section 5.1. Reasons for study treatment discontinuation specific to postdose cardiac monitoring are provided in Table 4. The Medical Monitor should be contacted before discontinuing a participant.

Table 4: Discontinuation of Study Treatment Related to Postdose Cardiac Monitoring

Reasons for Study Treatment Discontinuation Related to Postdose Cardiac Monitoring ^a

Participants who have a cardiovascular treatment-related symptomatic event (eg, chest pain, dizziness, palpitations, lightheadedness, shortness of breath, or syncope) associated with reduction of the heart rate or associated with clinically relevant 12-lead ECG changes at any time during the 4-hour monitoring period on Day 1 or Day 2 (as applicable).Participants who have not met the discharge criteria on Day 1 after ≥ 4 hours of extended monitoring, or Day 2 by 4 hours postdose.

^a All treatment discontinuations should be discussed with the Medical Monitor.

ECG, electrocardiogram

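### Protocol 9.4.2.1.2 sends every participant who needs extended cardiac monitoring on Day 1 to a second dose, including those whose treatment must stop under 5.1 and Table 4

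*Protocol*

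**What the plan says.** Three parts of the protocol govern a participant who fails the Table 3 discharge criteria 4 hours after the first dose.

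- **Section 5.1** has a permissive list followed by a mandatory one. The mandatory list opens by saying that "double-blind treatment must be discontinued for any of the following reasons". It includes a participant who has not met the discharge criteria on Day 1 after at least "4 hours of extended monitoring, or Day 2 by 4 hours postdose". It also includes a treatment-related cardiovascular symptomatic event accompanied by a heart-rate reduction or a clinically relevant ECG change during the 4-hour monitoring period.
- **Section 9.4.2.1.3 and Table 4** repeat both reasons. The discharge reason covers those who "have not met the discharge criteria on Day 1 after ≥ 4 hours of extended monitoring, or Day 2 by 4 hours postdose". The section adds: "A complete list of reasons for study treatment discontinuation is provided in Section 5.1". It also asks that the Medical Monitor be contacted before a participant is discontinued.
- **Section 9.4.2.1.2**, the text for managing extended monitoring, has four bullets. The first reads: "Vital signs will be assessed hourly and 12-lead ECG may be performed, as clinically indicated, until the participant meets the discharge criteria". The second says: "The Medical Monitor should be contacted if the participant does not meet the discharge criteria after" at least 4 hours of extended monitoring. The third says: "Any participant who requires extended monitoring on Day 1 must return on Day 2 for the second dose", with re-monitoring as on Day 1, and then: "These participants will be discontinued from study treatment if they do not meet the discharge criteria at 4 hours after the second dose". The fourth concerns symptomatic events without a heart-rate or ECG change.

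**The concern.** The third bullet of 9.4.2.1.2 has no exception and no pointer to 5.1 or Table 4. It applies to anyone who needed extended monitoring, and under the section's opening sentence that means anyone who failed at Hour 4. Read as written, it instructs the site to give a second dose to a participant whose treatment Section 5.1 says must already have ended.

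This is a matter of participant safety. By Table 3, a participant who still fails has a heart rate below 50 bpm with a fall of more than 10 bpm from predose, second-degree or higher AV block, or cardiac symptoms. Section 1.3 lists first-dose bradycardia and AV block among the events reported with this drug class. Section 9.4.2.1.2 is also the text that staff are likely to have in hand while managing the event, and it is the one that lacks the stop. Section 9.4.2.1.4 applies the first-dose procedures again when treatment restarts after an interruption, so the same uncertainty can recur there.

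**Working it through.** The plan gives no figure to reproduce. The check is a comparison of instructions for participants who need extended monitoring on Day 1.

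**Timing.** The discharge assessment is at Hour 4 (9.4.2.1.1). Four hours of extended monitoring bring the earliest time for the Day 1 stop to 4 + 4 = Hour 8. The protocol does not itself name Hour 8.

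| Situation | 5.1 and Table 4 | 9.4.2.1.2 | Agree? |
|---|---|---|---|
| No symptomatic-event stop; criteria met within 4 hours of extended monitoring | Not triggered | Second dose on Day 2, re-monitored | Yes |
| No symptomatic-event stop; criteria still unmet on Day 1 after at least 4 hours of extended monitoring | Discontinue | Contact Medical Monitor (bullet 2); second dose on Day 2 (bullet 3) | No |
| Symptomatic-event stop met in the first 4 hours, and extended monitoring needed | Discontinue (also stated in 9.4.2.1.1) | Second dose on Day 2 (bullet 3, read literally) | No |
| Second dose given; criteria unmet 4 hours later | Discontinue | Discontinue | Yes |

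**Second row.** The *or* in 5.1 and Table 4 makes the Day 1 failure sufficient on its own. Bullet 3 makes the second dose mandatory and ties discontinuation only to the Day 2 result. Followed literally, it leaves the Day 1 half of the rule with no effect.

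**Can the participant in the second row reach Day 2?** Yes. Bullet 1 continues hourly vital signs with no time limit until the criteria are met. Recovery and release after Hour 8 are therefore foreseen, and bullet 3 then tells that participant to return.

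**Does bullet 2 resolve it?** Not by its words. Contacting the Medical Monitor is not an instruction to stop treatment or to withhold the second dose. Section 9.4.2.1.3 gives the Medical Monitor no stated power to set 5.1 aside, and Section 9.1 does not allow protocol waivers or exemptions.

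**Third row.** Bullet 3 does not separate participants by why they failed at Hour 4. Someone who meets the symptomatic-event stop and also fails discharge falls within its wording.

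**The case against.** The best defence is that the sections work together. Bullet 2 brings in the Medical Monitor at exactly the Table 4 threshold. The next subsection asks for that contact before a discontinuation, lists the event as a reason to stop and points to 5.1 as the complete list. Section 9.1 also refers immediate safety concerns to the Medical Monitor for a decision on continuing. On this view bullet 2 is the first step of the stop, and bullet 3 speaks only of participants still on treatment. The symptomatic-event case supports this, since nobody would suppose the authors meant to redose that participant. This argument stands as evidence of intent. It does not supply the missing instruction, because bullet 3 says *any* and *must*, without a condition. Bullet 4, by contrast, makes discharge conditional on meeting the criteria.

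A second argument is that the Day 1 stop is open-ended: a participant who recovers at Hour 9 could be said to have met the criteria on Day 1 and so to escape it. That reading is available and would narrow the conflict. It would not remove it, since a participant who does not meet the criteria at all on Day 1 is still covered by bullet 3 without exception.

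Third, the practical risk is limited. Bullet 1 keeps the participant under observation until the criteria are met, and the second dose would be monitored as the first was. Sections 3.1 and 7 of the SAP say the study will be discontinued early, so fewer first doses may remain. All of this stands and bears on size. The SAP does not say that dosing has ended.

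**Conclusion.** The inconsistency is real. For a participant who has not met the discharge criteria on Day 1 after at least 4 hours of extended monitoring, 5.1 and Table 4 require treatment to stop while 9.4.2.1.2 requires a second dose. The same unqualified sentence reaches a participant already stopped for a symptomatic event. It should be corrected, although the stop is probably what was intended.

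The size cannot be put in numbers of participants, because the documents give no rate for failed discharge. The direct exposure at issue is one re-monitored dose, with the Medical Monitor already contacted. No endpoint, sample size or analysis is affected.

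Two stronger inferences are tempting and not supported:

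- A reader might infer that such a participant could go on to receive the rest of the 12-week course. That would need the site and the Medical Monitor to disregard 5.1 and Table 4 indefinitely.
- A reader might try to express the conflict as a share of Day 1 outcomes, as if all other outcomes were uniformly consistent. The symptomatic-event stop cuts across those outcomes, and a count of rule categories says nothing about how often they occur.

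The conclusion assumes that 5.1 states the intended rule, which its mandatory wording and its repetition in Table 4 support.

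**What to change.** Change 9.4.2.1.2 only.

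- **Second bullet**, replace with: *If discharge criteria are still unmet after ≥ 4 hours of extended cardiac monitoring on Day 1, contact the Medical Monitor and discontinue study treatment (Table 4); no second dose is given.*
- **Third bullet, first sentence**, insert after the mention of Day 1 extended monitoring: *and is not discontinued under Table 4*. The requirement to return on Day 2 and be re-monitored then applies only to participants still on treatment. Because Table 4 also lists the symptomatic-event stop, this insertion covers that case as well.

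The rest of the third bullet, and Sections 5.1 and 9.4.2.1.3, stay as they are.

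The cost is a wording amendment with the IRB/EC approval described in Section 11.1, and health authority approval if the change is judged substantial. It adds no assessment, visit or data item.

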9.4.2.1.3. Study Treatment Discontinuation Related to Postdose Cardiac Monitoring

A complete list of reasons for study treatment discontinuation is provided in Section 5.1. Reasons for study treatment discontinuation specific to postdose cardiac monitoring are provided in Table 4. The Medical Monitor should be contacted before discontinuing a participant.

Table 4: Discontinuation of Study Treatment Related to Postdose Cardiac Monitoring

Reasons for Study Treatment Discontinuation Related to Postdose Cardiac Monitoring ^a

Participants who have a cardiovascular treatment-related symptomatic event (eg, chest pain, dizziness, palpitations, lightheadedness, shortness of breath, or syncope) associated with reduction of the heart rate or associated with clinically relevant 12-lead ECG changes at any time during the 4-hour monitoring period on Day 1 or Day 2 (as applicable).Participants who have not met the discharge criteria on Day 1 after ≥ 4 hours of extended monitoring, or Day 2 by 4 hours postdose.

^a All treatment discontinuations should be discussed with the Medical Monitor.

ECG, electrocardiogram

